## **Sample size calculation:**

- Expected difference ( $\Delta\Delta$ ) = 0.4 g/kg BW
- Standard deviation ( $\sigma\sigma$ ) = 0.5 g/kg BW
- Significance level ( $\alpha\alpha$ ) = 0.05
- Power ( $1-\beta 1-\beta$ ) = 0.80
- With an expected difference of 0.4 g/kg BW and a standard deviation of 0.5, a minimum sample size of 25 per group is required.
- To ensure robustness and account for drop-outs and variability, targeting at least 28 participants per group is recommended.

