Since the hypotheses of the study are exploratory, no formal sample size calculation has been performed. This prospective observational study aims to recruit >60 multiple trauma patients.

Randomization:

Simple randomization method will be used to assign subjects into two groups A and B.

Group A – Nutrison Protein Plus with 6.3 g/100 ml protein

Group B - Nutrison Protein Intense with 10 g/100 ml protein

Ethical considerations:

This study will be conducted in full conformity with the Declaration of Helsinki and Good Clinical Practices.

Local ethical committee approval will be asked before any patient will be included.

Considering that nutritional support has become a standard-of-care in every intensive care unit in the world, it is considered that this research is based on collecting data routinely available for every critically ill patient. Although no intervention is performed an informed consent will be provided.

Taking into account that the included patients are not able to provide informed consent at the time of recruitment (on ICU admission), a Power of Attorney or a Legal tutor will act as Consultee and will be asked to consent/decline participation to the study on legal behalf of the patient. If patients have Advance Decision Plan including participation in research studies the Plan will be respected and recruitment pursued/abandoned accordingly.

After regaining capacity, all patients will be asked to provide Informed Consent for using their personal data and will be given the possibility to:

- Provide Informed Consent for the acute data and follow-up.
- Deny research participation and request destruction of acute data collected.

Study participant research data, which is for purposes of statistical analysis and scientific reporting, will be transmitted to the Data Manager and the Statistician of the study.

Expected impact of the study

KNOWLEDGE

Investigators aim to provide a detailed description of protein administration using two different types of enteral formulas. The main objectives of the study are to evaluate energy, protein intake and gastrointestinal tolerance while using enteral nutrition formulas with different protein content. Nevertheless, investigators want to provide data about the impact of these different enteral nutrition formulas on body composition as well as on functionality.

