### **2. Primary Outcome Analysis:**

- Differences in protein and calorie intake between the groups at day 5 and day 10 will be analyzed using independent t-tests or Mann-Whitney U tests, depending on the data distribution.
- Differences in residual gastric volume between the groups at day 5 and day 10 will be analyzed using independent t-tests or Mann-Whitney U tests.

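### The 28 per group said to cover drop-outs and variability keeps 80% t-test power for about 4 losses in total or an SD up to 0.525, but not both; the t-test minimum is 26, not 25

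*SAP*

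**What the plan says.** The SAP (Sample size calculation) takes a difference of 0.4 g/kg body weight, an SD of 0.5, a significance level of 0.05 and power of 0.80. It concludes: "With an expected difference of 0.4 g/kg BW and a standard deviation of 0.5, a minimum sample size of 25 per group is required". It then raises the target: "To ensure robustness and account for drop-outs and variability, targeting at least 28 participants per group is recommended". The visible text gives no loss rate, no range for the SD and no step leading from 25 to 28.

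For intake at day 5 and day 10, the SAP (2. Primary Outcome Analysis) says that group differences "will be analyzed using independent t-tests or Mann-Whitney U tests, depending on the data distribution".

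The protocol (Sample size calculation) calls the hypotheses exploratory, reports no formal calculation, and sets a different target: "This prospective observational study aims to recruit >60 multiple trauma patients".

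**The concern.** Power of 80% is the only power that the plan claims, and 28 per group is offered as protection for it against two separate threats: patients without an evaluable outcome, and an SD larger than assumed. The step from 25 to 28 is only three patients per group, and the starting figure of 25 comes from a formula that is slightly optimistic for the tests named.

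Some loss is foreseeable. Under the protocol's Ethical considerations, patients who regain capacity may decline and have their acute data destroyed. The population is ventilated patients with multiple trauma, and one of the two primary time points is day 10. If the margin is thinner than the text suggests, a non-significant result could be given more weight than the design supports.

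**Working it through.** **Inputs.** Difference 0.4, SD 0.5, alpha 0.05 and power 0.80 are from the SAP's sample size section; the tests are from its primary outcome section. Sidedness is not stated. Two-sided is assumed because it reproduces the SAP's figure. Equal groups are assumed except where shown. Loss rates are assumptions.

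**1. The plan's own figure.** Normal approximation: n = 2 × (1.960 + 0.842)² × (0.5/0.4)² = 24.53, rounded up to 25. One-sided: 2 × (1.645 + 0.842)² × (0.5/0.4)² = 19.3, so 20. The 25 is therefore reproduced as a two-sided normal-approximation result. The 28 would follow from an unstated 10% inflation: 25/0.90 = 27.8.

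**2. Power of the planned t-test.** Power comes from the noncentral t distribution with n₁ + n₂ − 2 degrees of freedom and noncentrality 0.4 / (0.5 × √(1/n₁ + 1/n₂)).

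| Evaluable per group | t-test power | Normal approximation |
|---|---|---|
| 25 | 79.1% | 80.7% |
| 26 | 80.7% | 82.2% |
| 27 | 82.2% | 83.6% |
| 28 | 83.6% | 84.9% |
| 30 | 86.1% | 87.3% |

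The t-test minimum is 26.

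**3. Mann-Whitney on normal data.** With an asymptotic efficiency of 0.955, power is 77.2% at 25, 78.9% at 26, 80.4% at 27 and 81.9% at 28. Simulation gives slightly less (79.7% at 27 and 81.3% at 28 in 40,000 trials). The minimum is 27 or 28.

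**4. Room for losses at SD 0.5 (t-test).** Equal losses of 2 per group leave 26 v 26, 80.7%; that is 2/28 = 7%. Unequal losses totalling 4 also hold: 27 v 25 gives 80.7% and 28 v 24 gives 80.5%. Five losses do not: 26 v 25 gives 79.95% and 28 v 23 gives 79.6%. The limit is about 4 in total.

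**5. Loss rates applied to 28 per group (assumed).**
- 10%: average power over independent binomial losses is 79.3%, with a 67% chance that power is below 80%.
- 15%: about 77%.
- 20%: about 74%.

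**6. Room for a larger SD.** With no losses, 28 per group holds 80% up to SD 0.525. At SD 0.55 power is 76.2%, and at 0.60 it is 68.8%. With 26 left the limit is SD 0.505, and at SD 0.55 power is 73.0%. By the SAP's own approximation, losing 3 per group leaves 25, where the SD limit is 0.505, so almost nothing remains for a larger SD.

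**7. The protocol's target.** More than 60 is about 30 per group: 86.1% with no loss, room for 4 losses per group (30 − 26), and SD up to 0.544. Average power at 10% loss is 82.1%. At SD 0.55 with no loss it is 79.1%.

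**The case against.** The strongest reply is that nothing here is miscalculated. The 25 is reproduced, 28 matches a conventional 10% allowance, and by the SAP's own approximation 28 tolerates 3 losses per group. The difference between the normal and t calculations is one patient per group, under 1 percentage point of power at 25, and the average shortfall at 10% loss is 0.7 point (80.0 − 79.3). All of that stands and sets the size of the point.

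The target of 28 is also a floor, and the protocol aims for more than 60. At about 30 per group the margin is clearly better. That stands too, but the SAP neither cites that target nor relies on it, and the protocol gives no calculation for it.

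The SAP (4. Missing Data) plans multiple imputation, so a lost outcome need not be a deleted patient. Imputation generally does not recover the information in a missing primary outcome, and it cannot restore destroyed records. Day 5, which has equal primary status, should lose fewer patients than day 10.

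Three stronger readings are not supported:
- A reader might infer that power fails as soon as either group loses more than 2. It does not: 28 v 24 still gives 80.5%. For the same reason, the chance that either group falls below 26 is not the chance that power falls below 80%.
- A reader might infer that Mann-Whitney leaves no room at all. At 27 per group, results fall on either side of 80% depending on the method, so the margin is zero to one per group. The SAP would choose that test when data are not normal, and it can then outperform the t-test.
- A reader might infer that the trial is badly underpowered. The protocol presents the hypotheses as exploratory, and the visible text gives no loss rate from which a serious shortfall could be shown.

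**Conclusion.** The point holds and is minor. The stated minimum of 25 per group falls just short of 80% under either planned test: 79.1% with the t-test and about 77% with Mann-Whitney on normal data. The 28 per group absorbs about 4 losses in total, or an SD about 5% above the assumed value (0.525/0.5), but not both. The statement that it covers both is therefore not borne out by the SAP's own inputs. The shortfall is under 1 point at 10% loss and reaches about 3 and 6 points at 15% and 20%.

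This rests on two-sided testing, on lost outcomes adding no information, and on assumed loss rates. The statement that no rate is given applies to the SAP text available for review, which lacks the part just before the sample size section.

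**What to change.** Revise the last two bullets of the SAP's sample size section, with no change in enrolment:
- State that the test is two-sided and that 26 evaluable patients per group give 80.7% power with the t-test (difference 0.4, SD 0.5). Note that 27 to 28 are needed if Mann-Whitney is applied to normal data.
- Replace the claim that 28 covers drop-outs and variability with the actual margin: 83.6% with complete data, and at least 80% with about 4 losses in total at SD 0.5.
- State the assumed loss rate at day 10 and give power over a range. From 28 per group: about 79%, 77% and 74% at 10%, 15% and 20% loss; 76.2% at SD 0.55 with no loss; 73.0% at SD 0.55 with 26 left.
- Reconcile 28 per group with the protocol's target of more than 60. If about 30 per group is the working target, say so and give its figures: 86.1% with no loss, 82.1% on average at 10% loss, and 79.1% at SD 0.55 with no loss.

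The cost is one paragraph and a slightly less favourable power statement. No extra patients and no change to the analysis are needed.

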## **Statistical Analysis:**

### **1. Descriptive Statistics:**

- Summary statistics (mean, standard deviation, median, interquartile range) will be provided for all continuous variables. Frequencies and percentages will be provided for categorical variables.

### **2. Primary Outcome Analysis:**

- Differences in protein and calorie intake between the groups at day 5 and day 10 will be analyzed using independent t-tests or Mann-Whitney U tests, depending on the data distribution.
- Differences in residual gastric volume between the groups at day 5 and day 10 will be analyzed using independent t-tests or Mann-Whitney U tests.

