Body composition monitoring

Objective:

This prospective observational randomized study aims to determine energy, protein intake and gastrointestinal tolerance while using enteral nutrition formulas with very high protein content and enteral nutrition formulas with normal protein content.

Outcomes will be assessed as:

Primary outcome parameter:

- Differences regarding achieving protein and calorie daily targets in grams per kilogram of body weight (g/kg BW) at day 5 of the intervention period and at day 10 when using enteral nutrition formulas with different protein content
- Differences regarding residual gastric volume when using enteral nutrition formulas with different protein content

Secondary outcome parameter:

Differences regarding body composition when using enteral nutrition formulas with different protein content:

- a) Quadriceps rectus femoris thickness measured by B-mode ultrasonography on admission, on day 5, on day 10 and 15.
- Body composition assessment (Fat-Free mass, Total Body water, Phase angle) using bioimpedance analysis after patient has been stabilized (24 hours after extubation and on day 5 after extubation)
- c) Plasmatic levels of prealbumin and inflammatory markers (C reactive protein) on day 5 and on day 10;
- d) Muscle function evaluation using handgrip dynamometer after extubation and sedation cessation. (24 hours after extubation and on day 5 after extubation)

Safety points:

- Clinical parameters vomiting, diarrhoea
- Biochemical parameters base excess, urea levels
- Daily gastric residual volume evaluation using ultrasound gastric antrum measurements after 24 hours of continuous enteral nutrition administration using both types of formulas;

Study population

Consecutive patients with multiple trauma intubated and mechanical ventilated, admitted to the intensive care unit (ICU).

Inclusion criteria:

- Adult patients (>18 yrs) admitted to the ICU
- Multiple trauma (Injury severity score > 18)
- Intubation and mechanical ventilation upon admission in ICU or during the first 24 hours of admission, for at least 48 h

Exclusion criteria

- Age < 18 years
- Pregnant women
- Patients not intubated or not mechanically ventilated or receiving only noninvasive ventilation
- o Patients with enteral feeding contraindication 48 h after admission
- o Patients with recent gastrointestinal surgical intervention
- Patients on chronic therapy with corticosteroids

Sample size calculation

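### The primary intake and residual-gastric-volume comparisons are valid but unadjusted; prespecifying a regression on age and Injury Severity Score would be a cheap and probable, though not certain, gain in precision

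*SAP*

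**What the plan says.** SAP section 2 (Primary Outcome Analysis) gives two rules. For intake: "Differences in protein and calorie intake between the groups at day 5 and day 10 will be analyzed using independent t-tests" or Mann-Whitney tests, chosen according to the data distribution. For gastric volume: "Differences in residual gastric volume between the groups at day 5 and day 10 will be analyzed using independent t-tests or Mann-Whitney U tests". Neither rule names a covariate or a model. The opening part of the SAP was not in the text available for review, so this describes the visible text only.

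The Protocol's Randomization section reads "Simple randomization method will be used to assign subjects into two groups A and B". It mentions no stratification or blocking.

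Three baseline variables matter here. Age and injury severity are inclusion criteria, the latter as "Multiple trauma (Injury severity score > 18", so both should be known at entry for every patient. Body weight appears only as the denominator of the intake outcome, "in grams per kilogram of body weight (g/kg BW"; the documents do not say when or how it is obtained.

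The SAP's sample size section assumes "an expected difference of 0.4 g/kg BW and a standard deviation of 0.5", and arrives at 25 per group, raised to 28.

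**The concern.** In an unadjusted comparison, any outcome variation that baseline variables could predict stays in the error term. A chance difference between arms in those variables also stays in the estimated formula effect. Simple randomisation of a small sample does nothing to limit such differences, so in this plan neither design nor analysis deals with them.

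Two things are at stake. One is the width of the confidence interval for the intake and gastric-volume contrasts. The other is discipline: if an imbalance shows up in the baseline table and covariates are added only then, their choice is driven by the data. Naming them in advance avoids this.

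**Working it through.** **Inputs.** From the SAP sample size section: difference 0.4 g/kg, SD 0.5 g/kg, alpha 0.05 (taken as two-sided), power 0.80, and 25 per group raised to 28. From the Protocol: simple randomisation (1:1 assumed) and more than 60 patients planned. Assumed, because the documents give no value: R², the share of within-arm outcome variance explained jointly by the covariates, from 0 to 0.30.

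**Step 1: reproduce the SAP's figure.** n = 2(1.96 + 0.84)² × 0.5² / 0.4² = 24.5, so 25 per group, as stated. The one-sided version gives 20, so the SAP's test is two-sided. The exact t version gives 26. At 28 per group the exact power of the unadjusted t-test is 83.6%.

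**Step 2: chance imbalance.** With N = 56 in equal arms, the SD of a standardised baseline difference is √(4/56) = 0.267. A difference above 0.5 SD lies 0.5/0.267 = 1.87 standard errors out, with probability about 6% for one given covariate. For at least one of three independent covariates it is 1 − (1 − 0.061)³ = 17%.

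**Step 3: gain and cost of adjustment.** Adjustment multiplies the residual SD by √(1 − R²). It also costs p degrees of freedom and, on average, inflates the variance by (N − 3)/(N − 3 − p) through chance covariate imbalance. With N = 56 and p = 3 that factor is 53/50 = 1.06, with 51 degrees of freedom. Power uses the noncentral t distribution; the half-width is t(0.975; 51) × 0.5√(1 − R²) × √(2/28 × 1.06).

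| Analysis at 28 per group | Power for 0.4 g/kg | 95% CI half-width (g/kg) |
|---|---|---|
| Unadjusted t-test | 83.6% | 0.268 |
| Adjusted, R² = 0 | 81.4% | 0.276 |
| Adjusted, R² = 0.05 | 83.3% | 0.269 |
| Adjusted, R² = 0.10 | 85.2% | 0.262 |
| Adjusted, R² = 0.20 | 89.0% | 0.247 |
| Adjusted, R² = 0.30 | 92.6% | 0.231 |

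**Step 4: break-even.** In variance terms three covariates pay for themselves when (1 − R²) × 53/50 < 1, that is R² > 3/53 = 0.057. With age and Injury Severity Score alone (p = 2) the condition is R² > 2/53 = 0.038.

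**Step 5: if only 25 per group are evaluable.** The unadjusted t-test has 79.1% power. With three covariates it is 76.4, 80.6, 84.9 and 89.3% at R² = 0, 0.10, 0.20 and 0.30.

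**Not computable.** The SAP gives no SD or target difference for residual gastric volume, so no gain can be stated for that outcome. The same holds for calories, since the g/kg figures point to protein.

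**The case against.** The case for leaving the plan alone is substantial.

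- *Validity.* Unadjusted tests are valid under randomisation, and chance imbalance is already reflected in their error rate and confidence interval. The planned t-test exceeds 80% power if 28 per group are evaluable, and the Protocol calls its hypotheses exploratory. This stands: there is no bias or type I error fault.
- *No evidence of prognostic strength.* No figure in the documents links age or injury severity to intake or gastric volume, and the entry threshold on the severity score narrows its range. This stands, and it is why the gain is given as a range that includes a loss.
- *Skewed data.* The SAP keeps a Mann-Whitney option. Replacing it with ordinary regression and no provision for skewness would lose something. This stands and is dealt with in the fix.

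A reader might go further and infer that adjustment is free. It is not: below R² of about 0.06, three covariates reduce precision.

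A reader might also infer that body weight is known before feeding and must predict intake, because it is the denominator. The documents do not record when weight is taken. The predictive argument also depends on how volume is set. Suppose delivered volume were unrelated to weight, mean intake were 1.2 g/kg and the weight CV were 15 to 20% (all assumptions). Weight would then explain roughly (1.2 × 0.15)²/0.25 = 13% to (1.2 × 0.20)²/0.25 = 23% of the variance. If volume is fully scaled to weight, the share is 0%. The Protocol frames the outcome as reaching per-kilogram targets, which points towards scaling.

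**Conclusion.** This is an efficiency and chance-imbalance improvement, not an error in the plan. In the visible text both primary comparisons are unadjusted, allocation is simple, and age and Injury Severity Score should be available at entry at no extra cost.

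For protein intake at 28 evaluable per group, three covariates would move power from 83.6% to between about 81% (R² = 0) and 93% (R² = 0.30). The range is asymmetric: about 2 points lost at worst, about 9 gained at R² = 0.30, and under 2 gained at R² = 0.10. These figures rest on the SAP's difference and SD, equal arms, a two-sided 5% test and an assumed R². It is reasonable to expect some gain, but the documents do not establish one.

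**What to change.** In SAP section 2, make the main analysis of each primary outcome (protein intake, calorie intake, residual gastric volume, at day 5 and at day 10) a linear regression on randomised group, age and Injury Severity Score. Enter both covariates as continuous and fix them before any outcome data are seen. Add body weight only if the plan also states that it is recorded before feeding starts.

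Report the adjusted mean difference with its 95% confidence interval. State in advance what will be done if residuals are clearly skewed: robust or bootstrap standard errors, or a transformed or rank-based outcome. Report the planned unadjusted t-test or Mann-Whitney result alongside.

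The cost is a few lines of SAP text and one degree of freedom per covariate. If three covariates turn out to explain nothing, the loss is about 2 points of power. No extra patients are needed, and no new data beyond dating the weight measurement if weight is used.

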### **3. Secondary Outcome Analysis:**

- Changes in quadriceps rectus femoris thickness over time will be analyzed using repeated measures ANOVA or mixed-effects models.
- Differences in body composition parameters (Fat-Free Mass, Total Body Water, Phase Angle) will be analyzed using paired t-tests or Wilcoxon signed-rank tests for within-group comparisons and independent t-tests or Mann-Whitney U tests for between-group comparisons.
- Differences in plasmatic levels of prealbumin and C-reactive protein will be analyzed using independent t-tests or Mann-Whitney U tests.
- Differences in handgrip strength will be analyzed using paired t-tests or Wilcoxon signed-rank tests for within-group comparisons and independent t-tests or Mann-Whitney U tests for between-group comparisons.

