ImpACt of very high protein Content enteral nUtrition formulas on protein metabolism and residual gastric volume in critically ill MUltipLe trAuma paTiEnts – ACCUMULATE trial -

Study Protocol

Imp**AC**t of very high protein **C**ontent enteral n**U**trition formulas on protein metabolism and residual gastric volume in critically ill **MU**ltip**L**e tr**A**uma pa**T**i**E**nts

- ACCUMULATE trial -

Background and rationale:

Despite an increased survival among critically ill patients, many of the ICU "survivors" may develop prolonged functional disabilities(1). It has already been proven that nutritional therapy is essential, considering that an adequate provision of calories and proteins may influence patients prognostic(1).

Multiple trauma patients are on a particular nutritional risk, since their high nitrogen demands and associated nutritional therapy challenges, caused by repeated surgical intervention or multiple imagistic procedures(2). Although nutritional therapy impact on mortality is still in debate, clear, positive results were obtained in decreasing ICU and hospital stay after adequate nutritional support(3).

According to ESPEN guideline on clinical nutrition in the ICU early enteral nutrition (within 48 h) should be initiated in order to assure an adequate calorie and protein intake(4). Beside optimal timing, the management of nutrition therapy in critically ill patients should also integrate the optimal route and caloric/protein targets(4).

Energy requirements monitoring through indirect calorimetry has been proposed as a standard-of-care method for critically ill patients, considering its proven superiority towards predictive equation(5).

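### Fat-free mass, total body water and handgrip have no pre-feeding reading, and the between-group tests adjust for nothing: valid, but less precise than they could cheaply be

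*SAP*

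**What the plan says.** **Timing (Protocol, Secondary outcome parameter).** Fat-free mass, total body water and phase angle are to be measured "using bioimpedance analysis after patient has been stabilized (24 hours after extubation and on day 5 after extubation". Handgrip follows the same schedule: "Muscle function evaluation using handgrip dynamometer after extubation and sedation cessation. (24 hours after extubation and on day 5 after extubation". Only quadriceps thickness, among the secondary outcomes, has an admission reading.

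**Why the first reading is on treatment.** Eligibility requires "Intubation and mechanical ventilation upon admission in ICU or during the first 24 hours of admission, for at least 48 h". The protocol background cites guidance that "early enteral nutrition (within 48 h) should be initiated".

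**Allocation (Protocol, Randomization).** "Simple randomization method will be used to assign subjects into two groups A and B". No stratification is mentioned, and adults of both sexes are eligible.

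**Analysis (SAP section 3).** For bioimpedance, "Differences in body composition parameters (Fat-Free Mass, Total Body Water, Phase Angle) will be analyzed using" paired tests within each arm and unpaired t or Mann-Whitney tests between arms. Handgrip is handled the same way: "Differences in handgrip strength will be analyzed using paired t-tests or Wilcoxon signed-rank tests for within-group comparisons and independent t-tests" or their rank equivalent. There is no covariate, no indexing to height and no sex-specific scaling. The SAP does not say whether the between-arm test uses the level at each visit or the change between the two visits.

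**Sample size (SAP, Sample size calculation).** The calculation is for protein intake only. No SD or expected effect is given for bioimpedance or handgrip.

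**The concern.** Absolute fat-free mass, body water and grip strength vary between people with sex, body size and age. Usually a baseline reading takes out much of that variation. Here none is possible before feeding, so the variation stays in the error term unless the model includes covariates that stand in for it. Simple randomisation of a small sample also leaves the arms free to differ in the proportion of women, and an unadjusted estimate carries that difference with it.

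At stake is how much the trial can say about body composition and functionality, which the protocol (Expected impact of the study) says it wants to describe. The sample size was not set for these outcomes, so any precision must come from the analysis. Adjustment is credible only if it is specified in advance. If it is added after an imbalance has been seen, it becomes a post hoc choice.

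The within-arm paired tests do not help. They remove stable body size, but they do not compare the formulas.

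**Working it through.** **1. The plan's own figure.** For protein intake, with difference 0.4, SD 0.5, two-sided alpha 0.05 and power 0.80: n per group = 2 × (1.960 + 0.842)² × (0.5/0.4)² = 24.5, so 25. This matches the SAP. (The exact t-test gives 25.5, so 26.) The SAP then targets at least 28 per group, which is used below.

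**2. Timing.** At least 48 h of ventilation plus 24 h after extubation puts the first bioimpedance or grip reading at least 72 h after intubation. If feeding starts within 48 h, as the cited guidance says, that reading comes after at least about 24 h of study formula.

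**3. Precision without adjustment.** Minimum detectable difference (MDD) at 80% power = (1.960 + 0.842) × SD × √(2/n).
- n = 28: 2.802 × 0.267 = 0.75 SD
- n = 20: 0.89 SD
- n = 15: 1.02 SD

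The last two apply if fewer patients reach the post-extubation visits.

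**4. Precision with adjustment.** If the covariates explain a share R² of the variance, the standard error is multiplied by √(1 − R²). The R² range is an assumption. Power is Φ(0.5 / [0.267 × √(1 − R²)] − 1.960) for a true difference of 0.5 SD, at 28 per group.

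| R² | SE multiplier | SE cut | MDD (SD) | Power for 0.5 SD |
|---|---|---|---|---|
| 0 | 1.00 | – | 0.75 | 46% |
| 0.3 | 0.84 | 16% | 0.63 | 61% |
| 0.5 | 0.71 | 29% | 0.53 | 75% |
| 0.7 | 0.55 | 45% | 0.41 | 93% |

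These figures ignore the lost degrees of freedom, which are few: residual 56 − 2 = 54 without covariates and 51 with three.

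**5. How much sex alone might explain.** Assume 70–80% men (proportion p) and a gap between the sexes of g = 1–2 within-sex SDs. Then R² = g²p(1 − p) / [1 + g²p(1 − p)]. The low end is 0.16/1.16 = 14% (g = 1, p = 0.8). The high end is 0.84/1.84 = 46% (g = 2, p = 0.7).

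**6. Chance imbalance in sex.** With 28 per group and 70–80% men, the arms differ by at least 10 percentage points with probability 40–47%, and by at least 20 points with probability 7–11% (exact binomial). With 61 patients, just above the protocol's target, and 25% women, simulated simple randomisation gives at least 10 points in 37% of trials and at least 15 points in 18%.

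**7. What a 10-point imbalance does to the estimate.** Take 61 patients, 25% women and a gap of g within-sex SDs. The shift is 0.10g, and the standard error is √(4/61) × √(1 + 0.1875g²).
- g = 1: 0.10 / (0.256 × 1.090) = 0.36 SE
- g = 2: 0.20 / (0.256 × 1.323) = 0.59 SE
- Upper limit for any g: 0.10 / √(0.1875 × 4/61) = 0.10/0.111 = 0.90 SE

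**8. Validity.** In 20,000 simulated trials with 28 per group, 75% men, a gap of 1.5 within-sex SDs and no formula effect, the unadjusted t-test rejected in 4.9%.

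**The case against.** The strongest reply is that an unadjusted comparison of randomised arms is a legitimate choice. It is unbiased on average, it keeps its 5% level (step 8), and its standard error already includes the spread due to sex and height. That stands. A reader might go further and infer that body size swamps any formula effect, or that a few extra women in one arm could create or reverse a finding. The documents do not support this. A 10-point imbalance moves the estimate by roughly 0.4–0.6 of a standard error and never more than 0.9, which the interval already allows for. Large effects remain detectable.

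A reader might also take it as settled that raw levels are compared. The SAP does not say so. Two visits would permit a between-arm test of change, which removes stable body size and could be precise: MDD = 0.749 × √(2 × (1 − 0.9)) = 0.335 SD if the two readings correlate at 0.9 (assumed). But a change score would start from a value already on treatment, so any formula effect before extubation would be partly or wholly subtracted. That answers a different question from the one the protocol poses.

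Three further objections stand:
- The size of the gain rests on assumed R², sex mix and sex gap.
- Neither document lists height as collected.
- The case for body-size adjustment is not made for phase angle.

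Finally, these are secondary outcomes in a study the protocol calls exploratory, which limits the importance of the point.

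**Conclusion.** The point holds as one about precision, not validity. Fat-free mass, total body water and handgrip have no pre-feeding value, and the planned between-arm tests carry no adjustment under simple randomisation. Adjustment would reduce the standard error by about 16–45% if sex, age and height explain 30–70% of the variance, equivalent to 1/0.7 = 1.4 to 1/0.3 = 3.3 times the patients. That range is an assumption, and nothing in the documents shows where in it recently extubated trauma patients fall.

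The unspecified choice between level and change is a gap in its own right and should be closed. The part of the SAP before its sample size section was not in the text available, so a covariate statement there cannot be ruled out.

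This is an optional, cheap improvement. It leaves the primary analyses untouched and does not address selection of the patients who survive to extubation and can be tested.

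**What to change.** In SAP section 3:

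- State that the arms are compared on the level at each post-extubation visit (24 hours and day 5), because a change score would start from an on-treatment value.
- For fat-free mass, total body water and handgrip, make the between-arm analysis a linear regression on randomised group plus sex and age, and height where recorded. A mixed model over both visits with the same covariates is an acceptable alternative. The same model may be used for phase angle.
- Report the adjusted mean difference with its 95% CI, and keep the unadjusted comparison as descriptive.

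The cost is SAP wording and two or three degrees of freedom. These matter little at 28 per group and somewhat more if only about 15 per group are measured (residual 30 − 2 − 3 = 25). Height must be recorded at admission if it is not already. No visit or outcome measurement changes.
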